##### **6.4.2.2. Lymph Node Response Rate**

The LNR will be summarized with 95% CI using the exact method based on the ITT and PP analysis sets using both the IRC assessments and investigators assessments.

The SPD and percent change in SPD from baseline to each subsequent assessment will be summarized using both the IRC assessments and investigators assessments. The best percent change from baseline during the study will also be summarized based on the first reader of each reader pair ([Gilead Protocol 101-09 Imaging Charter]) unless the adjudicator choose the second reader. The best percent change from baseline in SPD is defined as the largest decrease in tumor size while the subject was on-treatment. The baseline SPD will be the last value prior to the start of IDELA therapy. Note that for subjects who only have increases in tumor size from baseline, the smallest increase will be considered as the best change from baseline in SPD. Analyses will be conducted for the ITT and PP analysis sets.

A waterfall plot of best on-treatment percent change in SPD based on the IRC and investigators assessments will be provided. Individual records for measurable and nonmeasurable lesions will be listed in detail.

#### 6.4.2.3. Time to Response

TTR will be evaluated using both the IRC and investigators data based on ITT and PP subjects who achieve a CR or PR (or MR for WM subjects). TTR will be summarized using descriptive statistics.

#### 6.4.2.4. Overall survival

OS will be analyzed using the KM method and KM curves for OS will be provided based on the ITT analysis set. An on-study OS analysis will be performed by only including deaths that occur while a subject is on study treatment or within 30 days post-last study treatment. Furthermore, OS will be analyzed by including the long-term follow-up data and considering any death as an event. Data from surviving subjects will be censored at the last time that the subject was known to be alive.

#### 6.4.2.5. Health-Related Quality of Life

The FACT-Lym questionnaire includes subscales for physical well-being (PWB, 7 items), social/ family well-being (SWB, 7 items), emotional well-being (EWB, 6 items), functional well-being (FWB, 7 items) and additional concerns (Lymphoma Subscale, LymS, 15 items). The FACT-Lym scoring guide identifies those negatively stated items that must be reversed before being added to obtain subscale totals. Negatively stated items are reversed by subtracting the response from “4”. After reversing proper items, all subscale items are summed to a total, which is the subscale score. For all FACT-Lym scales and symptom indices, the higher score is associated with the better quality of life. The scores in the following items need to be reversed:

- Physical well-being: all individual items
- Social/family well-being: none
- Emotional well-being: 5 individual items (except for the second item, “I am satisfied with how I am coping with my illness”)

- Functional well-being: none
- Additional concerns: all individual items

The subscale scores will be a summation of each individual item score. If  $\leq 50\%$  of item scores are missing, the subscale score will be calculated by multiplying the sum of the item scores by the number of items in the subscale, then divided by the number of non-missing item scores. This imputes the missing scores by the mean of the non-missing scores within a subscale.

Prorated subscale score = [sum of item scores] x [N of items in subscale] / [N of items answered]

The following composite scores will be derived from the above subscale total scores:

- FACT\_Lym Trial Outcome Index (TOI, score range: 0-116) = PWB + FWB + LymS
- FACT\_G Total Score (score range: 0-108) = PWB + SWB + EWB + FWB
- FACT\_Lym Total Score (score range: 0-168) = PWB + SWB + EWB + FWB + LymS

The FACT-G and FACT-Lym Total scores will be set to missing if 20% or more of the included items are missing (eg, only calculated if at least 22 of 27 FACT-G items are completed) or any of the component subscales are missing. TOI scores are set to missing if any of the component subscales are missing.

If the baseline value is missing for subscale (ie, PWB, SWB, EWB, FWB and LymS), mean values of the corresponding subscale scores will be used to impute the baseline value. The mean and change from baseline in mean scores to each subsequent assessment will be summarized for the subscale and composite scores. The best change from baseline during the study, defined as the highest positive value among all post-baseline visits minus the baseline value, will also be summarized.

Each subject's lymphoma subscale score and FACT-General subscales (ie, PWB, EWB, SWB, and FWB) scores at each assessment will be compared to their baseline scores. The minimally important difference (MID) for the FACT-Lym subscale is 3-5 points (Hlubocky et al, in press) and the MID for FACT-General subscales is 2-3 points (Yost and Eton 2005). As recommended by Yost and Eton (2005), the high end of this range will be used for interpreting individual subject change. An increase of at least 5 points will be required as a definition of symptom improvement for the lymphoma subscale and 3 points will be required as a definition of symptom improvement for the FACT-General subscales. A decline of at least 5 points will define symptom worsening for the lymphoma subscale and a decline of at least 3 points will define symptom worsening for the FACT-General subscales. Time to symptom response will be assessed by defining the first occurrence of symptom improvement as an event. Subjects who do not experience a symptom improvement compared to baseline will be censored at their last available PRO assessment time. Time-to-event analyses will be performed using the KM method. The cumulative distribution function (CDF) of best (or worst) change from baseline will be also provided. For the MID improvement comparison in Lyms, subjects with baseline score  $>55$  will be excluded (ie, subjects with no room for improvement). For the MID improvement comparison in FACT-General subscales subjects with baseline score  $>57$  will be excluded.

A data listing for each individual item, the subscale scores and the composite scores will be presented for each subject at each visit.

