### **3.6. Missing Data and Outliers**

#### Missing Data

A missing data point for a given study visit may be due to any of the following reasons:

- A visit occurred in the window but data were not collected or were unusable
- A visit did not occur in the window
- A subject permanently discontinued from the study before reaching the window

In general, values for missing data will not be imputed unless methods for handling missing data are specified.

Missing data in Functional Assessment of Cancer Therapy: Lymphoma (FACT-Lym) will be handled according to the administration and scoring guidelines (Section 6.4.2.5).

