2.6.2.9	Time to Response - Investigator Assessments - by Refractory to Bendamustine	ITT Analysis Set
2.6.2.10	Time to Response - Investigator Assessments - by Number of Times Refractory to an Alkylating Agent	ITT Analysis Set
2.6.2.11	Time to Response - Investigator Assessments - by Number of Times Refractory to Rituximab	ITT Analysis Set
2.6.2.12	Time to Response - Investigator Assessments - by Suitability for Radioimmunotherapy	ITT Analysis Set
2.6.2.13	Time to Response - Investigator Assessments - by Region	ITT Analysis Set
2.6.3	Time to Response - Independent Review Committee (IRC) Assessments	Per Protocol Analysis Set
2.6.4	Time to Response - Investigator Assessments	Per Protocol Analysis Set
2.7.1	Percent Change in SPD - Independent Review Committee (IRC) Assessments	ITT Analysis Set
2.7.2	Percent Change in SPD - Investigator Assessments	ITT Analysis Set
2.7.3	Percent Change in SPD - Independent Review Committee (IRC) Assessments	Per Protocol Analysis Set
2.8.1	Overall Survival during Study Treatment	ITT Analysis Set
2.8.2	Overall Survival including Data from Long-Term Follow-Up	ITT Analysis Set
2.9.1	Health Related Quality of Life (HRQL) - Summary of Change in FACT-Lym Subscale Scores	ITT Analysis Set
2.9.2	Health Related Quality of Life (HRQL) - Summary of Symptom Improvement/Worsening [a] in FACT-Lym Subscale Scores	ITT Analysis Set
2.9.3.1	Health Related Quality of Life (HRQL) - Relation Between Symptom Improvement/Worsening and Best Overall Response - Independent Review Committee (IRC) Assessments	ITT Analysis Set
2.9.3.2	Health Related Quality of Life (HRQL) - Relation Between Symptom Improvement/Worsening and Best Overall Response - Investigator Assessments	ITT Analysis Set
2.10	Change in Karnofsky Performance Status	ITT Analysis Set
3.1.1	Overall Summary of Treatment-Emergent Adverse Events	ITT Analysis Set
3.1.1.1	Overall Summary of Treatment-Emergent Adverse Events - by Age	ITT Analysis Set

Table Number	Title	Analysis Set
3.1.1.2	Overall Summary of Treatment-Emergent Adverse Events - by Race	ITT Analysis Set
3.1.1.3	Overall Summary of Treatment-Emergent Adverse Events - by Gender	ITT Analysis Set
3.1.1.4	Overall Summary of Treatment-Emergent Adverse Events – by Region	ITT Analysis Set
3.1.2.1	Treatment-Emergent Adverse Events by System Organ Class, High Level Term and Preferred Term	ITT Analysis Set
3.1.2.1.1	Treatment-Emergent Adverse Events by System Organ Class, High Level Term and Preferred Term - by Age	ITT Analysis Set

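### Mean-filled FACT-Lym baselines are not kept out of the individual improvement and worsening labels or the lymphoma-subscale ceiling exclusion

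*SAP*

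**What the plan says.** All of this is in SAP Section 6.4.2.5 unless stated otherwise.

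- **Partly answered subscale.** If no more than half the items are missing, the score is prorated from the answered items: "This imputes the missing scores by the mean of the non-missing scores within a subscale".
- **Missing baseline subscale.** For each of the five subscales, "mean values of the corresponding subscale scores will be used to impute the baseline value".
- **Individual change.** Each subject's LymS and FACT-General subscale "scores at each assessment will be compared to their baseline scores". A rise of 5 points (LymS) or 3 points (FACT-General subscales) is improvement, and an equal fall is worsening. The first improvement is the event for time to symptom response.
- **Distribution.** "The cumulative distribution function (CDF) of best (or worst) change from baseline will be also provided".
- **Ceiling.** For the LymS improvement comparison, baselines above 55 are excluded ("ie, subjects with no room for improvement").

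Section 3.6 states: "In general, values for missing data will not be imputed unless methods for handling missing data are specified". For FACT-Lym it refers to the scoring guidelines and back to Section 6.4.2.5. In Section 13, Tables 2.9.3.1 and 2.9.3.2 carry the labels further: "Relation Between Symptom Improvement/Worsening and Best Overall Response".

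**The concern.** A group mean may be tolerable as a filler when a cohort's mean change is summarised. It cannot stand in for a subject's own starting point when that subject is to be called improved or worsened. No sentence in Sections 3.6 or 6.4.2.5 separates the two uses, so a programmer following the text would carry the filled value into every individual-level output.

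For affected subjects, the label then reflects whether the later score lies above or below the group, not whether the subject changed. The ceiling exclusion is also bypassed, because a filled value near the middle of the scale does not exceed 55 whatever the subject's true level. The outputs at stake are the label counts, best and worst change and its distribution, the time-to-improvement curve, and the tables relating the labels to best overall response.

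**Working it through.** **1. The plan's own figures.** Items run 0 to 4 and LymS has 15 items, so its maximum is 15 × 4 = 60. Check from the Trial Outcome Index range: 116 − 28 − 28 = 60. The ceiling is 60 − 5 = 55, which agrees with the SAP. A subject starting at 56 can gain at most 4 points.

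**2. Who is affected.** Proration covers up to half the items. The fill therefore applies only if at least 8 of 15 LymS items are blank, or at least 4 items in a 6- or 7-item subscale. The Schedule of Assessments in Section 1.2 has the first FACT-Lym at Visit 2 and none at screening, so a missed form leaves no earlier value.

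**3. What the fill does.** Let Y be a later score, B the subject's own baseline and M the cohort baseline mean. Then

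Y − M = (Y − B) + (B − M).

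The second term is the subject's distance from the group and has nothing to do with change.

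**4. Ceiling rule.** A subject constantly at c, with c from 56 to 60, is called improved if c − M ≥ 5. For c = 56 this needs M ≤ 51, and then it holds for every c up to 60. With an observed baseline the same subject would be excluded.

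**5. Size of the label error (LymS, one visit, no true change).** The SAP gives no standard deviation (SD), so these are assumed: between-subject SD 8, 10 or 12; within-subject SD 4, 6 or 8; normal scores.

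- P(labelled improved or worsened), filled baseline = 2 × [1 − Φ(5 / √(SDb² + SDw²))]. For SDb 8 and SDw 4: 5 / √80 = 0.559, giving 57.6%.
- P(labelled), own baseline = 2 × [1 − Φ(5 / (SDw√2))]. For SDw 4: 5 / 5.657 = 0.884, giving 37.7%.

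The fair benchmark is how often a second own baseline would change the label through measurement noise alone. Simulation of the three-way label at within-subject SD 4:

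| Between-subject SD | Labelled, filled | Disagrees with own-baseline label, filled | Disagrees, repeat own baseline | Excess (points) |
|---|---|---|---|---|
| 8 | 57.6% | 55.4% | 42.0% | about 13 |
| 10 | 64.2% | 59.7% | 42.0% | about 18 |
| 12 | 69.3% | 62.8% | 42.0% | about 21 |

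For between-subject SDs 8, 10 and 12, the excess is about 4, 6 to 7 and 9 points at within-subject SD 6, and about 0, 2 and 4 points at within-subject SD 8. It is zero when the two SDs are equal (correlation 0.5), because the group mean is then as close to the subject's true level as one noisy own measurement.

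**6. Size of the ceiling error.** Assumed cohort mean 40 to 50, between-subject SD 8 to 12, within-subject SD 4, whole-number scores.

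- Share with an observed baseline above 55, normal scores clipped to 0-60: 4.2% (mean 40, SD 8) to 33.2% (mean 50, SD 12). In the latter case about 23 of the 33 points are subjects piled at exactly 60.
- The same share under a truncated normal, P(55.5 < X < 60.5) / P(−0.5 < X < 60.5) with total SD √(SDb² + 16): 3.1% to 16.9%.
- Of those above 55 in the clipped model, called improved at one visit with no true change: 97.0% to 98.8% at mean 40, and 74.3% to 87.4% at mean 50.

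Multiplied through for 10 missing baselines in the clipped model: 10 × 0.042 × 0.970 = 0.4 to 10 × 0.332 × 0.874 = 2.9 subjects. For 2 missing baselines: 2 × 0.042 × 0.970 = 0.1 to 2 × 0.332 × 0.874 = 0.6. Under truncation with 10 missing, 0.3 to 1.7 subjects (10 × 0.031 to 10 × 0.169) would be wrongly kept, before counting how many are called improved.

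**The case against.** The strongest reply is that little is at stake. Proration leaves few missing baselines, the SAP gives no count, and HRQL here is a single-arm, descriptive secondary endpoint with no decision rule attached. By-subject listings of items and scores would let a reader trace a missing form. All of that stands, and it limits the point to a minor one.

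A reader might infer that the mean is undefined and that the fill therefore breaks the general rule in Section 3.6. The documents do not support that. A method is stated, if tersely, and the cohort baseline mean of the same subscale is its most natural reading. Naming the population and visit would help, but the lack is missing detail, not a contradiction.

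A reader might also take the 13 to 21 point excess as the expected effect. It holds only at within-subject SD 4, which nothing in the SAP establishes. The 55% to 63% disagreement is mostly ordinary noise, since a repeat own baseline already gives 42%. Likewise, the 33% above the ceiling depends on clipping, and the ceiling failure needs an assumed cohort mean of 51 or lower as well as the SAP's 60 and 55.

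Finally, the scoring guidelines cited in Section 3.6 are not available here and could contain a limit. Section 6.4.2.5, to which that section also points, contains none.

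**Conclusion.** The point holds as a minor defect in a stated rule. Followed as written, and reading the mean as the cohort baseline mean, the plan labels subjects without a usable baseline by their position relative to the group. It can also count as improved someone whom its own ceiling rule would exclude.

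The excess label disagreement is about 0 to 21 percentage points per affected subject, for between-subject SD 8 to 12 and within-subject SD 4 to 8. About 3% to 17% (truncated) or 4% to 33% (clipped) of affected subjects would have had a LymS baseline above 55. With 10 missing baselines, that is at most about 0.4 to 2.9 subjects wrongly kept and called improved at a visit, in the clipped model with no true change. The SDs, cohort means and missing counts are all assumptions. Neither the item-level proration nor the overall response rate test is in question.

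**What to change.** Add one or two sentences to SAP Section 6.4.2.5:

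- Individual improvement and worsening labels, best and worst change and its cumulative distribution, time to symptom improvement, and the LymS ceiling exclusion use only subjects with an observed or item-prorated baseline for that subscale. Report the number not evaluable for each subscale.
- If mean imputation is kept, it applies only to group-mean summaries, and the mean is the across-subject baseline mean of that subscale.

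The proration rule stays as it is. The cost is that a few subjects leave these descriptive analyses, which then assume that a missing baseline is unrelated to change. That assumption should be stated with the results.

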## 1.2. Study Design

Design Configuration and Subject Population	
This protocol describes a Phase 2, open-label, single-arm, 2-stage, efficacy, safety, and pharmacodynamic study of IDELA in subjects with previously treated iNHL that is refractory both to rituximab and to alkylating-agent-containing chemotherapy.
 
Eligible subjects will initiate oral therapy with IDELA at a starting dose of 150 mg BID given continuously. Treatment with IDELA will continue until tumor progression or unacceptable toxicity. Subjects will be followed in the clinic at 2-week intervals through the first 12 weeks of treatment, at 4-week intervals from 12 to 24 weeks of treatment, at 6-week intervals from 24 to 48 weeks of treatment, and at 12-week intervals thereafter. Tumor response will be evaluated at baseline; at 8, 16, and 24 weeks of therapy; and every 12 weeks thereafter according to standard criteria. The responses will be assessed by both the investigator and an independent review committee (IRC).
 
The study will be conducted in 2 stages using Simon's optimal 2-stage design. In Stage 1 of the study, 31 subjects will be enrolled; if <math>\geq 9</math> of these Stage 1 subjects have a tumor response, then the study will continue. In Stage 2, a further 69 subjects will be enrolled. With a total intended sample size of 100 subjects, the study has power <math>>0.90</math> to achieve a 1-sided significance level of 0.005 and will provide an ample safety database.

Treatment Groups	
Starting Dose: 150 mg BID
 
Reduced Dose -1: 100 mg, BID
 
Reduced Dose -2: 75 mg, BID

Key Eligibility Criteria	

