### 1.3. Sample Size and Power

Planned Sample Size	Up to 120 subjects may be enrolled in order to ensure enrollment of $\geq$ 100 subjects (31 in Stage 1, and 69 in Stage 2) who have a documented diagnosis of lymphoma, who have confirmed refractory disease, and who can be evaluated for tumor response with baseline and on-study scans (through the planned 24-week, follow-up tumor assessment).
Power Statement	The null hypothesis that the IRC-reviewed ORR is $\leq$ 20% will be tested against the alternative hypothesis that it is $\geq$ 39% (ie, $\sim$ 40%). Using Simon's optimal 2-stage design [Simon 1989], a sample size of 100 subjects has power $>$ 0.90 to achieve a 1-sided significance level of $<$ 0.005 and will provide an adequate safety database.
Actual Enrollment and Impact on Power	A total of 125 subjects have been enrolled into this study and this will provide $>$ 0.90 power to test the primary hypothesis.

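### Time to symptom response censors subjects who die or stop IDELA without improving, so Kaplan-Meier overstates on-treatment symptom improvement by an amount the SAP gives no rates to fix

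*SAP*

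**What the plan says.** SAP Section 6.4.2.5 defines the endpoint as follows: "Time to symptom response will be assessed by defining the first occurrence of symptom improvement as an event". Improvement means a gain of at least 5 points on the lymphoma subscale or at least 3 points on a FACT-General subscale. Everyone else falls under a single rule: "Subjects who do not experience a symptom improvement compared to baseline will be censored at their last available PRO assessment time". The estimator is also fixed: "Time-to-event analyses will be performed using the KM method". Death, progression and stopping drug before improvement get no separate treatment.

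Two other places determine how this rule works in practice:

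- Section 1.2 states: "Treatment with IDELA will continue until tumor progression or unacceptable toxicity". In its schedule of assessments, the FACT-Lym row is marked at Weeks 0, 4, 8, 12, 16, 20, 24, 30, 36, 42 and 48. It has no mark at Visit 16+, end of treatment or follow-up.
- Section 3.6 supplies no fallback: "In general, values for missing data will not be imputed unless methods for handling missing data are specified".

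Elsewhere the SAP does deal with death explicitly. Section 6.4.2.1 counts death within 30 days of stopping drug as an event for DOR and PFS.

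**The concern.** Kaplan-Meier assumes that a censored subject has the same later chance of the event as those still under observation. That is reasonable for a subject still on treatment at data cut-off or after the Week 48 questionnaire. It is not reasonable for a non-improver whose questionnaires ended because of death, progression or toxicity. A subject who has died cannot improve, and one who stopped because of progression or toxicity is unlikely to resemble those still doing well on drug.

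Health-related quality of life is a stated secondary objective, and the study has one arm. The absolute Kaplan-Meier probability and median are therefore the result itself, with no comparator in which a similar bias might offset. The error favours the drug: too many subjects appear to improve, and too soon.

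**Working it through.** **No figure to reproduce.** The SAP gives no expected rate, event count or precision for time to symptom response. The check therefore compares the planned estimator with the cumulative incidence under stated assumptions.

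**Inputs from the SAP.** Event, censoring rule and estimator come from Section 6.4.2.5. The last scheduled FACT-Lym is at Week 48 (Section 1.2).

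**Assumed inputs.** Hazards are constant and independent: *a* for improvement and *c* for leaving through death or permanent discontinuation. Central values are a = 0.10 and c = 0.05 per month. Months are weeks × 7 / 30.4375, so Weeks 12, 24 and 48 are 2.76, 5.52 and 11.04 months.

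**Formulas.**

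- What the planned rule estimates: 1-KM = 1 − exp(−a·t)
- Probability of improving before leaving: CIF = a/(a+c) × [1 − exp(−(a+c)·t)]

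**Week 48, all exits.** 1-KM = 1 − exp(−1.104) = 66.8% in every row.

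| Exit hazard c | Exited by Week 48 if none improved | CIF | Excess of 1-KM |
|---|---|---|---|
| 0.03 | 28.2% | 58.6% | 8.2 points |
| 0.05 | 42.4% | 53.9% | 12.9 points |
| 0.08 | 58.7% | 47.9% | 18.9 points |

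For c = 0.05: 0.10/0.15 × [1 − exp(−0.15 × 11.04)] = 53.9%.

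**Earlier times, c = 0.05.**

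- Week 12: 24.1% against 22.6%, an excess of 1.5 points.
- Week 24: 42.4% against 37.5%, an excess of 4.9 points.

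**Week 48, death as the only competing event.**

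- c = 0.005 (about 5% dead by Week 48 if none improved): 66.8% against 65.4%, an excess of 1.5 points before rounding.
- c = 0.02 (about 20% dead): 66.8% against 61.2%, an excess of 5.7 points.

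**Median.** The Kaplan-Meier median is ln 2 / 0.10 = 6.9 months. The CIF reaches 50% when 1 − exp(−(a+c)·t) = 0.5(a+c)/a. For c = 0.05 that gives exp(−0.15t) = 0.25, so t = 9.2 months. For c = 0.08 it gives exp(−0.18t) = 0.10, so t = 12.8 months, which is beyond Week 48.

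**Check on the visit grid.** A simulation used the FACT-Lym visits at Weeks 4 to 48 and censored at the last questionnaire. The assumed medians were 12, 24 or 48 weeks to improvement and 24, 48 or 96 weeks to exit. The excess at Week 48 ran from about 8 to 32 points. For example, with a median of 24 weeks to improvement and 48 weeks to exit, 1-KM was 0.75 and the cumulative incidence 0.565. With no competing exits the two estimates agreed.

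**Direction.** 1-KM is never below the cumulative incidence. It is above it whenever someone leaves through a competing event and others improve later. That does not depend on the assumed hazards.

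**The case against.** - **The SAP never calls 1-KM the proportion of treated subjects who improved.** This is true. Section 13 lists a separate Table 2.9.2, "Summary of Symptom Improvement/Worsening [a] in FACT-Lym Subscale Scores", and lists no table for time to symptom response. Section 6.4.2.5 also plans a cumulative distribution of best or worst change. None of these uses the censoring rule. A reader might infer that every symptom-improvement result is inflated. The documents do not support that; the point is confined to the time-to-event output, to which Section 6.4.2.5 still commits.
- **Only death rules out improvement.** After stopping drug, improvement is possible but unobserved, and whether stopping competes or censors depends on the target. This stands. A hypothetical target, improvement had everyone stayed on treatment, would be closer to Kaplan-Meier. But the SAP does not state that target, and it would still need censoring that is independent of outcome, which is implausible here.
- **Progression as such is not a competing event.** A reader might want every progression counted as one. Section 6.1 allows a single PD followed by SD or better, with substantial drug interruption, to be disregarded in best overall response. A subject who stays on study after such a PD can still complete FACT-Lym and improve, and counting the PD would discard that improvement.
- **The size is assumed and largest at the latest visit.** This stands. Earlier gaps are small, and if improvements come early the Week 48 gap shrinks too.
- **The schedule comes from an extracted table, and its footnote defers visit detail to protocol Section 7.2, which is not at hand.** This is a fair caution. However, the adverse-event row of the same table carries marks beyond Visit 15, so the blank cells for FACT-Lym are unlikely to be an artefact.

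**Conclusion.** The point holds for one descriptive secondary output. As specified, 1-KM overstates the probability of symptom improvement on treatment, and the Kaplan-Meier median understates the time to it. The direction is certain if any non-improver dies or permanently stops IDELA before others improve.

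The size cannot be derived from the SAP. Under the assumed hazards it could matter at Week 48 (about 8 to 19 points for all exits) and is modest earlier or for death alone. A single headline figure such as 13 points would be one assumed scenario, not a finding about this trial. No hypothesis test or decision depends on this analysis, and ORR, DOR, PFS and OS are unaffected. It should be corrected because the result is read in absolute terms in a single-arm study and errs in the favourable direction.

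**What to change.** Amend Section 6.4.2.5 as follows:

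1. State the target as the probability of symptom improvement while on treatment.
2. Estimate it by cumulative incidence (Aalen-Johansen). The competing events are death, and permanent discontinuation of IDELA for any reason including progression, when either comes before improvement.
3. Do not count a progression that does not end treatment as a competing event.
4. Censor at the last questionnaire only subjects without improvement who are still on treatment at data cut-off or after the last scheduled questionnaire.
5. Keep the Kaplan-Meier curve, if wanted, as a supplement labelled as assuming that censoring is independent of outcome.

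The cost is SAP wording and minor reprogramming. The last-dose and death dates are already used in Sections 4.3.1, 6.4.2.1 and 6.4.2.4, so no new data are needed. The reported improvement probability will be lower.

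### The baseline ceiling of >57 for the FACT-General subscales is above any attainable subscale score (28, or 24 for emotional well-being), so the exclusion never removes anyone

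*SAP*

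**What the plan says.** SAP section 6.4.2.5 builds each FACT-Lym subscale score by summing its items after reversing the negatively worded ones, which is done by subtracting from 4. The four general subscales are "physical well-being (PWB, 7 items), social/ family well-being (SWB, 7 items), emotional well-being (EWB, 6 items), functional well-being (FWB, 7 items"), and the lymphoma subscale (LymS) has 15 items. The FACT-G composite is given as "Total Score (score range: 0-108) = PWB + SWB + EWB + FWB".

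Each subscale is then compared with the subject's own baseline. Improvement on LymS needs a gain of at least 5 points. For the other four, "3 points will be required as a definition of symptom improvement for the FACT-General subscales".

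Two ceiling exclusions follow, one directly after the other:

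- LymS: "For the MID improvement comparison in Lyms, subjects with baseline score $>55$ will be excluded (ie, subjects with no room for improvement").
- FACT-General subscales: "For the MID improvement comparison in FACT-General subscales subjects with baseline score $>57$ will be excluded". No reason is printed for this one, and the SAP does not say how 57 was obtained.

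The table list in section 13 includes Table 2.9.2, "Summary of Symptom Improvement/Worsening [a] in FACT-Lym Subscale Scores".

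**The concern.** A ceiling exclusion should remove subjects whose baseline is so high that the required gain is impossible. A cut-off of 57 is more than twice the highest score that any FACT-General subscale can take. A program that follows the text would apply a filter that never triggers and raises no error.

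Subjects at ceiling on these four subscales would then stay in the improvement comparison, where they can only count as not improved. On LymS the same kind of subject is removed. The improvement proportions for LymS and for the FACT-General subscales would thus rest on different denominator rules, with nothing in the output to show it. If the slip is noticed only after results are known, correcting it means changing denominators post hoc.

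**Working it through.** **Inputs (all SAP section 6.4.2.5).** Items: PWB 7, SWB 7, EWB 6, FWB 7, LymS 15. Required gain: 5 points for LymS, 3 points for each FACT-General subscale. The item maximum of 4 is not stated outright but is implied by the reversal rule.

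**Item maximum checked against the stated composite ranges.** Maximum subscale score = 4 × number of items:

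| Subscale | Items | Maximum |
|---|---|---|
| PWB | 7 | 28 |
| SWB | 7 | 28 |
| EWB | 6 | 24 |
| FWB | 7 | 28 |
| LymS | 15 | 60 |

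- Trial Outcome Index: 28 + 28 + 60 = 116, as stated.
- FACT-G: 28 + 28 + 24 + 28 = 108, as stated.
- FACT-Lym total: 108 + 60 = 168, as stated.

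**LymS cut-off.** Maximum less required gain: 60 − 5 = 55. This reproduces the SAP's figure. Integer baselines of 56 to 60 are removed, and these are exactly the scores from which a 5-point gain is impossible.

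**FACT-General cut-off.** The same formula gives:

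- PWB, SWB, FWB: 28 − 3 = 25.
- EWB: 24 − 3 = 21.

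The SAP's 57 is not reproduced. Numerically it equals 60 − 3, the LymS maximum less the FACT-General MID. That would fit a carry-over slip, but the SAP does not show its derivation.

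**Can any other route give a baseline above 57?**

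- Prorating is allowed with up to half the items missing. The extreme cases are 4 of 7 items all scored 4, giving 16 × 7/4 = 28, and 3 of 6 items all scored 4, giving 12 × 6/3 = 24. The maxima do not move.
- A missing baseline is imputed by a mean of the corresponding subscale scores. A mean cannot exceed the maximum of its components.
- Reading 57 as a cut-off on the FACT-G total does not help. The sentence refers to subscales, and a total of 58 leaves 108 − 58 = 50 points of room.

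**Result.** The rule excludes 0 subjects. The integer baselines that stay in but cannot gain 3 points are 26 to 28 (PWB, SWB, FWB) and 22 to 24 (EWB).

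**Effect on the proportion.** Let f be the share of subjects at ceiling and p the improvement proportion among those with room to improve. With ceiling subjects retained, the reported proportion is (1 − f) × p. The SAP gives neither value. Assuming p = 40%:

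| f (assumed) | Reported proportion |
|---|---|
| 5% | 0.95 × 40% = 38% |
| 10% | 0.90 × 40% = 36% |
| 20% | 0.80 × 40% = 32% |

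In counts, section 1.3 reports that "A total of 125 subjects have been enrolled into this study". If all 125 were in the denominator, f = 20% would be 25 subjects at ceiling and 100 with room. Forty improvers would then be reported as 40/125 = 32% instead of 40/100 = 40%.

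**The case against.** The arithmetic is hard to dispute. The case on the other side concerns how much it matters.

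- **Low stakes.** The study has a single arm, no test is specified for quality of life, and no decision depends on these proportions. Item, subscale and composite scores are listed for every subject and visit, so a corrected figure could be recomputed later. This stands and limits the reach of the point. It does not make the rule work, and recomputing after the results are known is weaker than fixing the rule beforehand.
- **Bias depends on the intended quantity.** The proportion of all subjects who gain at least 3 points is a legitimate description, and section 3.7 makes the analysis set the default denominator. The no-room rationale is printed only for LymS. This stands in part: the shortfall is relative to the rule's evident purpose. But the SAP does specify an exclusion here, and the specified exclusion has no effect.
- **The affected output is not fully pinned down.** The SAP does not define the improvement comparison or its denominator. The title of Table 2.9.2 could cover all five subscales or LymS alone. Nor is it said whether either exclusion applies to time to symptom response, where subjects who do not improve are censored. This stands.
- **The size is unknown.** The 40% and the 5% to 20% are assumptions, and f may be close to zero for some subscales. Using 125 also assumes that every enrolled subject was dosed and contributes quality-of-life data. This stands. The only magnitude that the document itself supports is that the rule removes no one.

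**Conclusion.** The rule is wrong as written. From the SAP's own item counts and score ranges, no FACT-General subscale baseline can exceed 28 (24 for EWB), so a cut-off of 57 is inoperative, while the adjacent LymS rule works as intended. No other part of the SAP corrects it.

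The direction follows from the algebra: whenever any subject is at ceiling and some of the others improve, the FACT-General improvement proportions come out lower than among subjects with room to improve, and they are not comparable with the LymS proportion. How much lower depends on a ceiling share that the SAP does not give.

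The effect is confined to a secondary descriptive summary. The primary response-rate analysis, the mean changes, the cumulative distribution functions and the worsening definitions are not touched. It should be fixed, but it does not threaten the trial's main conclusion.

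**What to change.** In section 6.4.2.5, replace the single cut-off of 57 with baseline >25 for PWB, SWB and FWB, and >21 for EWB, each being the subscale maximum less the 3-point MID. State that the reason is the same as for LymS. These values assume that the LymS logic was meant to carry over. If it was not, the sentence should be deleted and the denominator for the FACT-General proportions stated explicitly.

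It would also help, as a separate clarification, to say whether the ceiling exclusions (LymS and FACT-General) apply to time to symptom response and to Tables 2.9.3.1 and 2.9.3.2.

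The cost is one SAP sentence and two programming constants, with no new data. The FACT-General improvement denominators would shrink by the number of subjects at ceiling on each subscale.
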